8.1. Drugs (trade and generic, dosage, route of administration)

1. Epidiolex (cannabidiol) 100mg/ml oral solution given in a one time only single dose of either Group 1:10mg/kg OR Group 2: 20mg/kg (Research)
2. Placebo oral solution developed in a similar taste and appearance as the Epidiolex (Research)
3. Rescue Medication (Ibuprofen 600mg or acetaminophen/codeine 650/60mg if contraindication to Ibuprofen); as needed post-study intervention per provider discretion (Research)

8.2. Devices

8.3. Biologics

8.4. Laboratory Tests

Urine pregnancy test (Research)
Urine toxicology (drug screen; Research)

8.5. Imaging Procedures**8.6. Other Research Procedures (e.g., other safety and efficacy assessments.)**

Medical History and Demographics (Routine care)
Oral Examination w/ vitals (Routine care)
Pain, Psychoactive and Sleep scale Questionnaires (Research)
Randomization to one of three study groups: Group 1) Epidiolex 10mg/kg; Group 2) Epidiolex 20mg/kg; Group 3) Placebo (Research)
Planned dental treatment (Routine care)

8.7 Attach a Schedule of Activities (SOA) [Excel File](#) [Download the Template here: [Schedule of Activities](#)]

Check to indicate that the SOA Excel File is attached →

**9. Preparation/Handling/ Storage/Accountability of Investigational Drug, Biologic, or Device**

N/A - This study does not include any investigational products (e.g. drugs, devices or biologics)
 N/A - An Investigator Brochure is attached
 N/A - A Drug/Device Manual is attached

9.1. Acquisition and accountability

State how the study intervention and control product will be provided to the investigator. Describe plans about how and by whom the study intervention will be distributed, including participation of a drug repository or pharmacy, and plans for disposal of expired or return of unused product.

Local Walgreens Pharmacy will provide the drug and placebo at requested intervals during the study to study team who will oversee drug accountability, storage and administration. The study medication in both concentrations and the placebo will be provided by the pharmacy in a multi-use vials, ready to be drawn from according to the patient height/weight once a patient is randomized. Approved study staff will safely discard any remaining medication in the bottle when expired in accordance with the university drug disposal policy. When study recruitment has been completed, all remaining study drug will be discarded in the same manner.

9.2. Formulation, Appearance, Packaging, and Labeling

Describe the formulation, appearance, packaging, and labeling of the study intervention and control product, as supplied. Information in this section can usually be obtained from the IB or the package insert, or device labeling. This section should include the name of the manufacturer of the study intervention and control product.

Epidiolex is manufactured by GW Pharmaceuticals. EPIDIOLEX is a strawberry flavored clear, colorless to yellow solution supplied in a 105 mL amber glass bottle with a child-resistant closure containing 100 mL of oral solution (NDC 70127-100-01). Each mL contains 100 mg of cannabidiol. EPIDIOLEX is packaged in a carton with two 5 mL calibrated oral dosing syringes and a bottle adapter (NDC 70127-100-10). The pharmacy will provide the Epidiolex in a multi-dose vial to be drawn upon when the patient is randomized. Placebo will appear in a similar form.

9.3. Product Storage and Stability

Describe storage and stability requirements (e.g., protection from light, temperature, humidity) for the study intervention and control product. For studies in which multi-dose vials are utilized, provide additional information regarding stability and expiration time after initial use (e.g., the seal is broken).

Store EPIDIOLEX in an upright position at 20°C to 25°C (68°F to 77°F); excursions are permitted between 15°C to 30°C (59°F to 86°F). [See USP Controlled Room Temperature]. Do not freeze. Keep the cap tightly closed. Use within 12 weeks of first opening the bottle, then discard any remainder.

9.4. Preparation

Describe the preparation of the study intervention and control product, including any preparation required by study staff and/or study participants. Include thawing, diluting, mixing, and reconstitution/preparation instructions in this section. For devices, include any relevant assembly or use instructions.

Following randomization, study staff will retrieve the study drug or placebo bottle and prepare the amount based on patient's randomization group and weight/height. Study staff will prepare the dose in a 10ml calibrated syringe and wrap it with non-transparent tape so patient and clinician are blinded to the amount/type of medication used. Placebo will be prepared in the same manner, thus blinding the clinician study staff to study product used.

10. Study Intervention Additional Details

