
CBD is currently being tested in ~155 clinical trials for various disorders, with 16 of those trials assessing pain outcomes including one new study assessing analgesic efficacy of CBD after tooth extractions (www.clinicaltrials.gov, accessed March 2020). By an unusual regulatory circumstance, synthetic CBD is a Schedule I drug, whereas hemp-derived CBD is a Schedule V drug. Accordingly, we propose to use the FDA-approved cannabis-derived CBD (Epidiolex, Greenwich Biosciences, CA). Epidiolex is the first, and thus far only, FDA-approved Schedule V CBD oral solution designated for rare forms of epileptic seizures. The objective here is to test Epidiolex off-label for the treatment of emergency tooth pain in a human clinical trial. We hypothesize that Epidiolex will provide substantial pain relief for the patients presenting with emergency odontalgia in our clinical research facility.
			

5. Study Design			
5.1. Number of Groups/Arms	3	Group name(s)	1. CBD 10mg/kg single dose (given one time only) Epidiolex 100mg/ml oral solution 2. CBD 20mg/kg single dose (given one time only) Epidiolex 100mg/ml oral solution 3. Placebo oral solution single dose (given one time only)

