5.2. Overall Design Select all applicable			

	Randomization				Cluster Randomized								
	Group-Sequential				Adaptive Design								
	Parallel Design				Placebo-Controlled								
	Superiority				Equivalence				Non-inferiority				
Device			Pilot			Pivotal				Post-Approval			
Drug/Biologic			Phase 1		Phase 1/2		Phase 2		Phase 2/3		Phase 3		Phase 4
 Dose escalation		If yes, details →											
 Dose ranging		If yes, details →		10mg/kg single dose (given one time only) Epidiolex 100mg/ml oral solution vs. 20mg/kg single dose (given one time only) Epidiolex 100mg/ml oral solution									
 Sub-studies		If yes, details →											
5.3. Other Design Details: Double-arm phase II randomized placebo-controlled trial with quadruple masking (Participant, Care Provider, Investigator, Outcomes Assessor)													

6. Study Population

6.1. Study Population(s) Label/Name To add more populations – select a row, copy & paste	6.2. Identify the criteria for inclusion The criteria that every potential participant must satisfy, to qualify for study entry. All individuals in this study population must meet all of the inclusion criteria in order to be eligible to participate in the study	6.3. Identify the criteria for exclusion The characteristics that make an individual ineligible for study participation. All individuals in this study population meeting any of the exclusion criteria at baseline will be excluded from study participation.

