Adults 18-75 years old with moderate-severe odontogenic pain	
 -Healthy adults 18-75 years old, ASA I or II. -Permanent tooth with moderate to severe odontogenic pain, i.e. ≥30 on a 100mm VAS, as reported verbally by the patient. -Clinical pulpal diagnosis of irreversible pulpitis or pulpal necrosis, and periapical diagnosis of symptomatic apical periodontitis. -Test negative for recent cannabis use and/or other drugs of abuse including alcohol (urine tests collected at screening visit. Results will be available on site within 3-5 minutes). -Participant able to understand the forms (English or Spanish) and provide informed written consent 	
 -ASA Class III or IV, patients with hepatic impairment, pregnant or lactating women (pregnancy test is performed at the screening visit). -Patients on drugs metabolized by enzymes that also metabolize CBD (e.g. clobazam, diazepam, topiramate, warfarin), or other drugs known to interact with Epidiolex (as assessed by PI at time of screening). -Self-reported prior experience inhaling cannabis (either via smoking or vaporization). -Use of opioids in the month prior to screening/treatment visit, and/or NSAIDS or acetaminophen 6 hours prior to treatment. -Unwilling to participate
6.4. Will screen failures be allowed to re-screen at a later date?	 No  Yes If yes, describe criteria below ↓	Since the patients present with emergency pain and their pain will need to be addressed in a timely manner with appropriate treatment, there won't be any re-screening.

7. Study Intervention(s) being tested or evaluated

This can include prevention, diagnostic or therapeutic interventions (e.g., drug or device) or educational, health services or basic science interventions (e.g., educational program, health care delivery model, or examining basic physiology)

This is a therapeutic intervention study where the FDA approved study drug used off-label in two different doses according to randomization will be assessed against a Placebo of similar taste and appearance.

Group 1: CBD 10mg/kg single dose (given one time only) Epidiolex 100mg/ml oral solution

Group 2: CBD 20mg/kg single dose (given one time only) Epidiolex 100mg/ml oral solution

Group 3: Placebo oral solution single dose (given one time only)

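### At 100 mg/mL the 10 and 20 mg/kg doses need different numbers of 10 mL fills above 50 kg, so the taped syringe in 9.4 does not secure care-provider masking to dose level

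*Combined protocol and SAP*

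**What the plan says.** Section 5.3 describes the trial as having "quadruple masking (Participant, Care Provider, Investigator, Outcomes Assessor").

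The dose-ranging entry in 5.2 reads "10mg/kg single dose (given one time only) Epidiolex 100mg/ml oral solution vs. 20mg/kg single dose (given one time only) Epidiolex 100mg/ml oral solution". Sections 5.1 and 7 list the arms in the same terms: "CBD 10mg/kg single dose (given one time only) Epidiolex 100mg/ml oral solution" and "CBD 20mg/kg single dose (given one time only) Epidiolex 100mg/ml oral solution". Section 8.1 repeats 100 mg/mL for either dose, and 9.2 gives the product strength: "Each mL contains 100 mg of cannabidiol".

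Section 9.4 makes the amount depend on randomization group and on weight and height, and then states: "Study staff will prepare the dose in a 10ml calibrated syringe and wrap it with non-transparent tape so patient and clinician are blinded" to the amount and type of medication. Placebo is to be prepared in the same way, but no placebo volume is given. The section has no rule for doses above 10 mL, no volume matching and no fixed number of syringes.

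Section 9.1 contains a different description of supply: "The study medication in both concentrations and the placebo will be provided by the pharmacy in a multi-use vials". No second concentration is defined in the text available.

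Under 10.2 a licensed dentist gives the study product, and either a dentist or a registered nurse monitors the participant for three hours.

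**The concern.** If both active doses come from one strength, the higher dose always has twice the volume of the lower. Wrapping a syringe can conceal how full it is. It cannot conceal that a second syringe or a refill was needed. Weight is measured for dosing, so a dentist who knows it can work back from the number of fills to the dose level.

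This matters because dose ranging is a stated design feature, 12.3 compares the three groups with each other, and 12.2 says the pilot is to supply the effect size for a definitive trial. If the dosing dentist also monitors, knowledge of dose level could affect how firmly participants are encouraged to wait 60 minutes before rescue (11.1), or how adverse events are elicited. Section 12.4 analyses both time to rescue and adverse events. Any distortion of the 10 versus 20 mg/kg contrast would carry into the planning of the next trial.

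**Working it through.** The plan states no volume or fill count, so there is no figure of its own to reproduce.

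**Inputs.** Doses of 10 and 20 mg/kg at 100 mg/mL (5.1, 5.2, 7, 8.1, 9.2); syringe capacity 10 mL (9.4). Eligibility sets no weight limit.

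**Formulas.** Volume (mL) = weight (kg) × dose (mg/kg) ÷ 100 mg/mL. Fills = volume ÷ syringe capacity, rounded up.

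10 mg/kg gives 0.1 mL/kg, which reaches 10 mL at 100 kg. 20 mg/kg gives 0.2 mL/kg, which reaches 10 mL at 50 kg.

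| Weight (kg) | 10 mg/kg (mL) | 20 mg/kg (mL) | Fills of 10 mL |
|---|---|---|---|
| 45 | 4.5 | 9.0 | 1 vs 1 |
| 50 | 5.0 | 10.0 | 1 vs 1 |
| 55 | 5.5 | 11.0 | 1 vs 2 |
| 70 | 7.0 | 14.0 | 1 vs 2 |
| 100 | 10.0 | 20.0 | 1 vs 2 |
| 120 | 12.0 | 24.0 | 2 vs 3 |
| 150.1 | 15.01 | 30.02 | 2 vs 4 |

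The counts differ at every weight above 50 kg. At or below 50 kg both doses fit one syringe, and only weaker cues remain, such as plunger position and the volume itself.

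**Carton syringes.** Section 9.2 says the product is "packaged in a carton with two 5 mL calibrated oral dosing syringes". Using these does not remove the cue: 1 vs 2 fills at 50 kg, 2 vs 3 at 70 kg and 2 vs 4 at 80 kg.

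**Share of participants affected (assumed weights).** Take normal weights with mean 60-90 kg and SD 12-20 kg.
- Lowest share, mean 60 and SD 20: z = (50 − 60)/20 = −0.5, so P(>50 kg) = 0.69, or about 15 of 22 per arm.
- Highest share, mean 90 and SD 12: z = (50 − 90)/12 = −3.33, so P(>50 kg) exceeds 0.99, or nearly all 22.

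**If 9.1 did mean two strengths in a 2:1 ratio (an assumption).** At 70 kg:
- 50 and 100 mg/mL: 700/50 = 14 mL and 1400/100 = 14 mL.
- 100 and 200 mg/mL: 700/100 = 7 mL and 1400/200 = 7 mL.

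The volume cue between the active arms disappears in either case. In the first case both volumes still exceed one 10 mL syringe above 50 kg.

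**The case against.** The strongest counter-argument is the wording on concentrations in 9.1. With two strengths in a 2:1 ratio the active volumes would be equal and this cue would vanish. It cannot be excluded, but no second strength is defined, and 5.1, 5.2 and 7 attach 100 mg/mL to each dose. On either reading the text needs correcting. The checkbox states in section 9 cannot be read, so an attached drug manual with more detail can be neither confirmed nor ruled out.

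It is also fair that the route to bias is conditional. The dentist must notice the fill count, relate it to weight, also take part in monitoring (a nurse may do so instead), and then behave differently. The contrast necessarily exposed is 10 versus 20 mg/kg, whereas the only hypothesis in 12.1 is that the drug relieves pain.

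A reader might infer more than the documents support:
- **That participants are unmasked.** Nothing shows that a participant would know what a given number of fills means.
- **That active can be told from placebo.** This depends on the placebo volume. If it matched one active arm, the fill count would separate placebo from the other active arm only. As no volume is stated, neither exposure nor protection can be shown.
- **That the results would be biased.** VAS pain is patient-reported, and no passage says the dosing dentist monitors or assesses. Bias is possible, not demonstrated.

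**Conclusion.** The concern holds in a limited form and should be fixed. On the plan's own figures, following 9.4 as written gives the dosing dentist a cue to dose level in every participant above 50 kg. The section therefore does not achieve the blinding to amount that it aims for, or secure the care-provider masking in 5.3. The volumes and fill counts are exact at 100 mg/mL. The share affected, about 69% to over 99%, rests entirely on the assumed weight distributions. Confidence is medium, because 9.1 leaves the concentration unreconciled and supporting documents may exist that cannot be seen. The finding is a gap in the masking procedure for the dose contrast. It is not evidence of a broken blind for participants or of a distorted comparison with placebo.

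**What to change.** 1. Reconcile the wording on concentrations in 9.1 with the single 100 mg/mL strength in 5.1, 5.2, 7, 8.1 and 9.2.
2. State in 9.4 the volume per kg and the number of syringes for all three arms, including placebo, and cover doses above 10 mL.
3. If there is one strength, make total volume and the number and size of wrapped syringes the same in every arm by adding placebo solution, with the assigned mg/kg unchanged. One layout is two syringes of 0.1 mL/kg each: active + placebo, active + active, placebo + placebo. At 70 kg this is 7 + 7 mL in each arm. Each syringe holds its share up to 100 kg; above that, every arm gets the same added syringes.
4. Check the taste match first. Placebo is only said to resemble the active product in taste, so with separate syringes only the 10 mg/kg arm would swallow two different liquids, which could create a new cue for the participant. Combining the volumes would avoid this, if the pharmacy confirms that it is acceptable.
5. If volumes cannot be matched, a partial alternative is that the dosing dentist takes no part in monitoring or assessment where existing staff allow. Sections 5.3 and 9.4 should then not claim care-provider masking to dose level.

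**Cost.** Protocol wording, slightly longer preparation, and more placebo solution. For 22 participants in the 10 mg/kg arm at an assumed mean weight of 60-90 kg, this is 22 × 0.1 × 60 = 132 mL to 22 × 0.1 × 90 = 198 mL. It doubles to 264-396 mL if placebo had been planned at 0.1 mL/kg and must also rise to 0.2 mL/kg. Participants in the lower-volume arm or arms swallow more liquid, 7 mL more at 70 kg. No extra participants are needed.

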10.1. Measures to Minimize Bias: Randomization and Blinding

This section should contain a description of randomization and blinding procedures (if applicable to the study design). It should include a description or a table that describes how study participants will be assigned to study groups, without being so specific that blinding or randomization might be compromised. Plans for the maintenance of trial randomization codes and appropriate blinding for the study should be discussed. The timing and procedures for planned and unplanned breaking of randomization codes should be included. Include a statement regarding when unblinding may occur and who may unblind. Provide the criteria for breaking the study blind or participant code. Discuss the circumstances in which the blind would be broken for an individual or for all participants (e.g., for serious adverse events (SAEs)). Indicate to whom the intentional and unintentional breaking of the blind should be reported.

REDCap will be utilized to create the randomization for treatment arm for all participants. Limited data will be entered into the REDCap software which will create a unique Study ID# for each participant. Randomization will also occur in REDCap per individual unique Study ID# created by the software.

Unblinding of a subject who has experienced an adverse event will be conducted by the PI by review of the online system of that particular subject's study e-chart and will occur within 24 hours of the AE notification. The PI will document and assess the unblinded information and appropriately report the AE, additionally make the appropriate treatment recommendations for the patient to ensure safety. In the case of serial adverse events of a similar type, or with a serious adverse event, the PI will unblind all participants and report to the IRB as required.

We will collect subject names and phone numbers to be recorded in the Participant Log in order to track when patients are scheduled for their regular clinic visits as research data collection will be linked to these regularly scheduled visits.

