
1. Primary outcome measure: a.VAS pain intensity differences from baseline among the groups at each time point and maximum pain relief.
 
b.Bite Force measurement using the Bite Fork at baseline, 1.5 h, 3h and 7d.
 
2. Secondary outcome measure: Measure psychoactive effects, mood changes at 0, 1.5h and 3h points, and somnolence at 3h and 1- week time point.
	
1. Patients will report their pain level using a 100mm Visual Analogue Scale (VAS) at 0, 15min, 30min, 45min, 1h, 1.5h, 2 and 3 hour and 1week post-administration visit time of study drug Epidiolex or Placebo.
 
2. Patients will report their pain level that is elicited by biting down on the Bite Fork at 0, 1.5h, 3h and 1week post-administration visit time of study drug Epidiolex or Placebo.
 
2. Patients will report feelings of drug high, alterations in internal perception and alterations in external perception, along with alertness, contentment and calmness by completing the following questionnaires:
 
a. Bowdle questionnaire b. Bond & Lader Mood Scale c. Epworth Sleepiness Scale
	
1. The VAS has been shown to be sensitive to changes in a patient's pain experience, is easily understood and easy to use. It has been successfully used in various health fields in children and adults.
 
2. The bite force measurement provided additional pain information being able to isolate one particular tooth (the problem tooth) being studies.
 
2. The three listed questionnaires are commonly used for psychedelic assessment and safety assessment of cannabinoids use, with a longstanding administration in previous published studies in medical journals such as "Pain", "CNS Drugs", and "Journal of Psychopharmacology". Such effects are not commonly associated with CBD use because of the inherent nature of the absence of THC based on current literature. Nevertheless, patients that report such adverse events at the end of the observation period will be asked to have a family member to accompany them home.

4. Rationale Briefly state the reason for conducting the clinical trial.			

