The following coding system will be used to ensure that participant identities remain confidential and to protect against disclosure. Each participant will be assigned a unique Study ID# and all study data collected will be coded with this number. The Study ID# will be linked to participants' names on the Participant Log which will be kept in a secure location separate from the coded study data and will be accessible only to members of the research team. Data collected for this study will be coded with a Study ID# and securely stored in the offices of the research team. Certain personal identifiers required to conduct the study but not for statistical analysis (name and phone numbers) will be kept separate from research data collected and not entered into REDCap. Certain personal identifiers such as date of birth and gender that are needed for statistical analyses will be entered into REDCap. REDCap is password-protected and HIPAA-compliant. Data entered into REDCap is stored on a secure UT Health server. All electronic data will be protected using password-protected computers. Government or university staff may review this study to make sure it is being conducted safely and legally.

The PI will be informed by study staff of any subject who experience an adverse event, whether during the study visits or during the one-week post-procedure time. The PI will proceed with unblinding of the subject's group. Depending on the nature and severity of the adverse event, the patient will be instructed to contact their physician or visit the urgent care clinic.

8. Protocol-Directed procedures, items, services or tests

List all procedures directed by the study plan - including items or services provided as part of routine or conventional care and those needed to diagnosis or treat research related complications.

Important Note – The protocol directed procedures listed must match those in the [Schedule of Activities \(attachment\)](#)

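### Section 10.1 has the PI break the code for any adverse event before assessing it, and open every code after one serious event; this undercuts Investigator masking and conflicts with Sections 11.1 and 11.2

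*Combined protocol and SAP*

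**What the plan says.** Section 5.3 describes the trial as having "quadruple masking (Participant, Care Provider, Investigator, Outcomes Assessor". Four sections then say when the code is opened.

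- **Section 7.** "The PI will be informed by study staff of any subject who experience an adverse event", at a visit or in the following week. The next sentence begins "The PI will proceed with unblinding of the subject" and sets no condition. Nature and severity appear only in the sentence after that, on referral to a physician or urgent care. Section 7 says nothing about when the event is assessed.
- **Section 10.1, individual break.** "Unblinding of a subject who has experienced an adverse event will be conducted by the PI", within 24 hours of notification. Then: "The PI will document and assess the unblinded information and appropriately report the AE". A purpose is given, to "make the appropriate treatment recommendations for the patient to ensure safety", but no condition that the allocation be needed for it.
- **Section 10.1, whole trial.** "In the case of serial adverse events of a similar type, or with a serious adverse event, the PI will unblind all participants". No count, period or definition of similarity is given for serial events.
- **Section 11.1.** If a serious event appears more than three times in one arm, that arm is discontinued and the PI unblinds the cases.
- **Section 11.2.** Unblinding of the subject's group depends on the nature and severity of the event.

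Section 3.3 also treats psychoactive effects, a secondary outcome, as adverse events. For "patients that report such adverse events at the end of the observation period" the only planned action is an escort home.

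**The concern.** A procedure for breaking the code does not contradict masking; every blinded trial needs one. The difficulty is that this one is routine and wide. Under Section 10.1 any adverse event, however mild, leads to a break, and the masked PI assesses and reports the event knowing the arm. One serious event, or an unstated number of similar events, also opens the codes of participants who had no event.

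Section 11.1 gives the PI oversight of safety monitoring, source document review and the decision to discontinue, and Section 12.4 compares adverse events between groups. At stake is whether those judgements are made blind, as Section 5.3 promises. Staff also have conflicting instructions on when to open a code and whose.

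**Working it through.** The plan gives no figure for this point. The check is a comparison of the sections, followed by illustrative arithmetic.

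**1. Two test cases.**

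- *One mild adverse event.* Section 10.1: unblind within 24 hours, then assess and report. Section 7: unblind, with no order of assessment stated. Section 11.2: unblind or not, according to nature and severity. A psychoactive report at three hours meets the literal trigger in 10.1, although an escort home does not require the allocation.
- *First serious event.* Section 10.1: open all codes. Section 11.2: open the subject's group, which may mean the subject's assignment or the whole arm; either is narrower than all participants. Section 11.1: open the cases after a fourth serious event in an arm. That step would be redundant if every code had been opened at the first.

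**2. Is the wide scope needed for safety?** Each participant receives one dose (Sections 5.1 and 11.1), so opening other participants' codes changes nobody's later dosing. The 11.1 rule counts serious events by arm, so it needs the allocation of those cases only.

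**3. Size.** Inputs: 22 per group (Section 12.2) and three groups (Section 5.1), so n = 3 × 22 = 66. All event rates below are assumptions.

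- *Individual breaks*, expected number 66p: at any-event rates of 5%, 10% and 20%, this is 3.3, 6.6 and 13.2 participants.
- *At least one serious event*, 1 − (1 − p)^66: at 0.1%, 0.5% and 1%, this is 0.064, 0.282 and 0.485.
- *Section 11.1 trigger*, four or more of 22 in at least one of three arms (binomial, counting participants): about 0.001% at 0.5% and 0.02% at 1%. At a 1% rate the two rules therefore act with probability 48% and 0.02%.
- *Serial events*, binomial with n = 66 and one event type affecting 1%, 2%, 3% or 5%. If two participants suffice: 0.141, 0.381, 0.593, 0.848. If three: 0.029, 0.146, 0.318, 0.647. At a fixed 2% rate, the undefined word alone moves the probability from 15% to 38%.

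**4. How many opened codes could still matter?** With sequential enrolment and the first serious event at participant K, E[K − 1 | K ≤ 66] = (1 − p)/p − 66(1 − p)^66 / [1 − (1 − p)^66]. At 0.1%, 0.5% and 1% this gives 32.1, 30.7 and 28.9 enrolled participants without a serious event. Follow-up ends at one week, however. The accrual period is not stated; if 66 are enrolled evenly over 6, 12 or 24 months, the number dosed in the preceding seven days is 66 × 7/182.5 = 2.5, 66 × 7/365 = 1.3 or 66 × 7/730 = 0.6.

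**The case against.** The strongest reply is that little harm can be traced. VAS, bite-fork pain and the psychoactive scales are reported by the participant. Events reach the PI from staff or from the participant's survey before the code is opened, and Section 12.4 plans chi-square tests of adverse events with no analysis of grading. This is a convenience-sample pilot. All of that stands and keeps the point modest.

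Section 10.1's template text also asks when the blind would be broken for one participant or for all, with serious events as its example. The sponsor gave a cautious answer for an off-label drug. The caution is reasonable, but step 2 shows that the wide scope adds no protection.

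The difference between Sections 7 and 11.2 may be only punctuation: the wording is nearly the same, with a full stop before the severity phrase in one and not in the other. That is plausible, so it should not be read as two deliberate policies. It does not reconcile Section 10.1 with either 11.1 or 11.2.

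A reader might infer three stronger things that the documents do not support:

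- *The pain results are biased.* An event reported at the end of observation comes after the 0 to 3 hour measures, and for that participant only the one-week measures remain. Nothing says that participants are told their arm.
- *Later allocations become predictable.* Assignments are generated in REDCap and no blocking is described. Knowing past allocations does not show the next one.
- *About 30 compromised participants.* That number comes from an assumed enrolment model, and most of those participants would have completed follow-up. It is not a measure of bias.

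**Conclusion.** The point holds at modest size. As written, Section 10.1 removes PI masking for any adverse event before assessment and reporting, and for everyone after one serious event or an undefined cluster. The order of break and assessment rests on Section 10.1 alone. This undercuts Section 5.3 and cannot be reconciled with 11.1 and 11.2.

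What is affected is the PI's handling of adverse events, and PI masking during source review and discontinuation decisions. At assumed serious-event rates of 0.1% to 1%, whole-trial unblinding has probability 6% to 48%; these figures depend entirely on the assumed rates. Only about 0.6 to 2.5 participants would still be contributing data at that moment, assuming even accrual over 24 to 6 months. The text is clear; the practical consequence is less certain, because actual event rates are unknown. The change is worth making because it is cheap and gives up no needed safety information.

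**What to change.** State one rule and use it in Sections 7, 10.1, 11.1 and 11.2:

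- (a) Break an individual code only when the allocation is needed to manage that participant, or when the event is serious.
- (b) Record severity and causality before opening the code, unless this would delay emergency care.
- (c) Delete the provision to unblind all participants, and open only the affected cases.
- (d) For a cluster of similar non-serious events, set a number, for example three participants, at which the PI may open those cases only. Word this as a named exception to (a).

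The PI keeps immediate access to the allocation of every serious case, which is what the arm-stopping rule in 11.1 needs.

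The cost is wording in four sections and a short severity and causality entry before each break, with no added staff or visits. The downside is that the PI manages isolated mild events blinded and sees a non-serious cluster by arm only once the stated number is reached.
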